6.0 STUDY DESIGN AND DESCRIPTION

6.1 Study Design

This is a phase 3, randomized, double-blind, parallel-group, placebo-controlled study in subjects with CIC as determined by the Rome III Diagnostic Criteria for Functional Constipation [4].

This study consists of a 14-day Screening Period and a subsequent 4-week (28 days) Double-Blind Treatment Period in which subjects will receive either lubiprostone or matching placebo twice a day. Subjects will be randomized to either active lubiprostone or placebo in a 1:1 ratio.

During the Screening Period, the defecation behavior of each subject is recorded in a diary to confirm he/she has constipation. Use of all existing laxatives is stopped at the beginning of the Screening Period (Visit 1). Subjects are instructed not to change their diet or lifestyle habits during the study. A total of 10 mg of bisacodyl suppository (or any equivalent drug) may be prescribed as a standard rescue medication if a subject has no adequate bowel movement for 3 consecutive days during the Screening Period of the study. When bisacodyl suppository does not improve constipation, glycerin enema (or equivalent drug) will be given. Subjects are instructed to complete their diaries before using rescue medications.

The subject diary will be distributed on Study Days -15, -1, 8 and 15. Subjects will be instructed to keep the diary every day including on the morning of Visit 1.

If the rescue medications fail to improve constipation, the investigator may decide to use another rescue medication. The recommendation may include a medication from the excluded medication list other than any form of polyethylene glycol (PEG), linaclotide, methylnaltrexone, or prucalopride, all of which are considered prohibited rescue medications. No rescue medication may be given 24 hours prior to and until 48 hours after the first dose of the study drug (Day 1). Subjects who use a rescue medication within 24 hours before the first dose of study drug on Day 1 should be withdrawn from the study. Those who use a rescue medication within 48 hours after dosing on Day 1 will be discontinued from the study by the investigator. The dose and mode of administration of rescue medications must be recorded in the electronic case report form (eCRF).

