7.2 Exclusion Criteria

Any subject who meets any of the following criteria will not qualify for entry into the study:

1. The subject has received any investigational compound within 30 days prior to Screening.

2. The subject has received lubiprostone in a previous clinical study or as a therapeutic agent.
3. The subject is an immediate family member, study site employee, or is in a dependent relationship with a study site employee who is involved in conduct of this study (eg, spouse, parent, child, sibling) or may consent under duress.
4. The subject has, in the judgment of the investigator, clinically significant abnormal hematological parameters of hemoglobin, hematocrit, or erythrocytes at Screening.
5. The subject has a history or clinical manifestations of significant mechanical obstruction (intestinal obstruction due to tumor, hernia etc).
6. The subject has a history of hypersensitivity or allergies to lubiprostone or any of its excipients.
7. The subject has a history of drug abuse (defined as any illicit drug use) or a history of alcohol abuse within 1 year prior to the Screening Visit.
8. The subject is required to take excluded medications as listed in Section [7.3.1](#).
9. If female, the subject is pregnant or lactating or intending to become pregnant before, during, or within 1 month after participating in this study; or intending to donate ova during such time period.
10. Subject whose constipation is considered to be due to drugs or to whom a prohibited concomitant medication has been administered.
11. Subject having chronic constipation due to a secondary cause (medications, diabetes mellitus, hypothyroidism, depression, etc).
12. Subject in whom there is sufficient criteria for irritable bowel syndrome (IBS) or functional defecation disorder.
13. Subject whose SBM frequency is 3 or more per week.
14. Subject whose SBM frequency has been less than 3 times per week for less than 6 months in duration or whose symptoms associated with SBM have been present for less than 6 months (hard feces, sensation of incomplete evacuation, or straining).
15. Subject who received treatment with a rescue medication within 24 hours prior to the first dose on the morning of Day 1: bisacodyl suppository, which is a standard laxative, glycerin enema, or any other rescue medication.
16. Subject who has megacolon/megarectum or has received a diagnosis of intestinal pseudo-obstruction.

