7.3.2 Drugs Permitted with Condition

7.3.2.1 Exceptions to Excluded Medications

If subject has a confirmed diagnosis of clinical depression and he/she has been treated with selective serotonin reuptake inhibitors (SSRIs), serotonin-norepinephrine reuptake inhibitors (SNRIs), or monoamine oxidase (MAO) inhibitors, treatment must have been at a stable dose for at least 30 days prior to the Screening Visit and not likely to change during the study. Antidepressants must not be suddenly stopped or reduced as doing so may provoke withdrawal symptoms or other untoward symptoms. The investigator determines how to handle subjects using antidepressants on an individual subject basis without compromising the safety of the subject.

Rescue medication use is determined and prescribed depending on the subject's clinical condition. 10 mg of bisacodyl suppository may be prescribed as a standard rescue medication if a subject has no adequate bowel movement for 3 consecutive days during the study. When bisacodyl suppository does not improve constipation, glycerin enema (or any equivalent drug) may be given.

Subjects are instructed to complete their diaries before taking rescue medications. No rescue medication may be used within 24 hours before and 48 hours after the start of the Double-Blind Treatment Period (Day 1).

Subjects who use a rescue medication within 24 hours before the first dose of study drug on Day 1 should be withdrawn from the study. Those who use a rescue medication within 48 hours after dosing on Day 1 will be discontinued from the study by the investigator. The dose and mode of administration of rescue medications must be recorded in the eCRF.

The use of excluded medications with exceptions mentioned above should be documented as concomitant medications, as applicable. The Sponsor's medical monitor or designee must be notified in advance (or as soon as possible thereafter) of any instances in which any drugs

permitted with condition are taken, or to be taken. Continued participation of the subject will be at the discretion of the Sponsor.

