13.1.1 Analysis Sets

Total Set

The total set consists of all subjects who signed the informed consent form including subjects withdrawn prior to randomization (defined as not randomized subjects).

Full Analysis Set

This will consist of all subjects randomized to receive study treatment whether or not they received treatment. Subjects will be assigned to the randomized treatment group regardless of treatment received.

Per-protocol analysis set

The Per-Protocol (PP) population will consist of subjects in the FAS with the additional following criteria for exclusion:

- Did not receive study treatment as per randomization schedule.
- Dose of randomized treatment was not adjusted.
- Violated inclusion criteria, such as:
 - Does not have a history of constipation defined as SBM frequency of less than 3 times per week on average for 6 months or longer (and observed during Screening Period).
 - Does not have SBMs with ≥ 1 of the following 3 symptoms for the last 6 months or longer, in at least 1 out of every 4 bowel movements: scybala stool or hard feces, straining, or the sensation of incomplete evacuation.
 - The subject rarely has loose stools without the use of laxatives.
- Violated exclusion criteria, such as:
 - The subject has a history or clinical manifestations of significant mechanical obstruction (intestinal obstruction due to tumor, hernia etc).

- Has chronic constipation due to a secondary cause (medications, diabetes mellitus, hypothyroidism, depression, etc).
- Has sufficient criteria for IBS or there is a functional defecation disorder.
- SBM frequency is 3 or more per week.
- SBM frequency has been less than 3 times per week for less than 6 months in duration or whose symptoms associated with SBM have been present for less than 6 months (hard feces, sensation of incomplete evacuation, or straining).
- Received treatment with a rescue medication within 24 hours prior to the first dose on the morning of Day 1.
- Has megacolon/megarectum or has received a diagnosis of intestinal pseudo-obstruction.
- Has confirmed or suspected organic disorders of the large intestine (obstruction, stenosis, carcinoma, or inflammatory bowel disease). Any subject in whom total colonoscopy has detected a polyp requiring treatment is excluded from this study.
- Has been hospitalized for gastrointestinal or abdominal surgery within 3 months before the start of this study.

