7.2 ANALYSIS SETS

Total Set: The total set consists of all subjects who signed the informed consent form, including subjects withdrawn prior to randomization.

Full Analysis Set (FAS): This will consist of all subjects randomized to receive study treatment whether or not they received treatment. Subjects will be reported according to their randomized treatment group regardless of treatment received.

Per-Protocol Analysis Set (PPS): The PPS will consist of subjects in the FAS with the additional following criteria for exclusion:

- Did not receive study treatment as per randomization schedule (including not receiving any randomized treatment)
- Dose of randomized treatment was adjusted.

CROSS-REGIONAL TEMPLATE

Template Number: C-TMPL-DO-801

Page: 11 of 28

Version Number: 1.2

Effective Date: 14 Sep 2015

This version replaces: 1.1

Parent Document: C-SOP-DO-800

Template Title: Statistical Analysis Plan (Legacy Takeda)

- Violated inclusion criteria, such as:
 - Does not have a history of constipation defined as SBM frequency of less than 3 times per week on average for 6 months or longer (and observed during Screening Period).
 - Does not have SBMs with ≥ 1 of the following 3 symptoms for the last 6 months or longer, in at least 1 out of every 4 bowel movements: scybalum stool or hard feces, straining, or the sensation of incomplete evacuation.
 - The subject rarely has loose stools without the use of laxatives.
- Violated exclusion criteria, such as:
 - The subject has a history or clinical manifestations of significant mechanical obstruction (intestinal obstruction due to tumor, hernia etc).
 - Has chronic constipation due to a secondary cause (medications, diabetes mellitus, hypothyroidism, depression, etc).
 - Has sufficient criteria for IBS or there is a functional defecation disorder.
 - BM frequency is 3 or more per week.
 - SBM frequency has been less than 3 times per week for less than 6 months in duration or whose symptoms associated with SBM have been present for less than 6 months (hard feces, sensation of incomplete evacuation, or straining).
 - Received treatment with a rescue medication within 24 hours prior to the first dose on the morning of Day 1.
 - Has megacolon/megarectum or has received a diagnosis of intestinal pseudo-obstruction.

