 - Has confirmed or suspected organic disorders of the large intestine (obstruction, stenosis, carcinoma, or inflammatory bowel disease). Any subject in whom total colonoscopy has detected a polyp requiring treatment is excluded from this study.
 - Has been hospitalized for gastrointestinal or abdominal surgery within 3 months before the start of this study.
 - Use of any excluded medications, procedures or treatments prior to the assessment of the primary endpoint.

Any other significant event interfering with efficacy evaluation of primary endpoint, to be decided at a Targeted Data Review Meeting. Definitions of criteria constituting major deviations will be provided, prior to unblinding.

CROSS-REGIONAL TEMPLATE

Template Number: C-TMPL-DO-801

Page: 12 of 28

Version Number: 1.2

Effective Date: 14 Sep 2015

This version replaces: 1.1

Parent Document: C-SOP-DO-800

Template Title: Statistical Analysis Plan (Legacy Takeda)

Subjects will be reported in according to their treatment group. Since subjects not receiving treatment per the randomization schedule are excluded from the PPS, this will be their actual treatment.

Safety Analysis Set (SAF): This will consist of all subjects who receive study treatment. Subjects will be assigned to the treatment group according to the actual treatment received.

The FAS will be used for efficacy analyses. Supportive analyses based on the PP will be performed for the primary efficacy variable. The SAF will be used for all safety analyses.

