7.8.1 Primary Efficacy Endpoint(s)

The primary efficacy endpoint is SBM frequency at Week 1; an SBM is defined as any BM that does not occur within 24 hours after rescue medication use. Since rescue medication use will be disallowed during Week 1, the SBM frequency should equal the BM frequency. In the case of protocol violators, the analysis will be based on SBMs.

In order to adjust for early withdrawals or those with less than 7 days diary data, weekly SBM frequency will be calculated as follows:

$$7 \times (\text{Number of SBMs} / \text{Number of days}),$$

where the number of days is the number of days during the week that the subject was in the study. Weeks will be calculated as 168-hour intervals starting from the day after randomization (Day1), if there is no time recorded for the morning dose on Day1 then the time of the first recorded morning dose will be used. The number of days will generally be 7 unless a subject drops out during a treatment week. If the number of days is less than 4, then the data will be considered insufficient and the frequency will be missing.

Primary Analysis

Since outliers are commonly observed in these data, parametric models may not be robust. The efficacy data will therefore be analyzed by a van Elteren test stratified by center. If necessary, small centers will be pooled as mentioned above. This procedure will test the null hypothesis of equal SBM rates between treatments at the end of Week 1 versus the alternative hypothesis of non-equality between the 2 groups; the test will be conducted at a 2-sided significance level of 0.05. A related 95% confidence interval and point estimate will be provided for the treatment difference; the confidence interval will be estimated by inverting the hypothesis test. This endpoint will be analyzed for the FAS.

Sensitivity Analyses

The primary analysis as described above will be repeated using the PP rather than the FAS. An additional sensitivity analysis using the FAS assuming a ‘worse-case’ scenario approach will also be conducted, where missing values, including those with < 4 days diary data, are assigned the worst case values (the lowest SBM frequency for week 1) recorded in the study by any subject for that endpoint at that time.

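### SAP 7.2 sets a per-protocol exclusion on BMs where the protocol uses SBMs, and SAP 7.8.1 misstates the Week 1 rescue ban; the FAS primary analysis is unaffected

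*SAP*

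**What the plan says.** **Frequency exclusion.** Among the violations that remove a subject from the PPS, SAP 7.2 lists "BM frequency is 3 or more per week". The matching bullet in Protocol 13.1.1 reads "SBM frequency is 3 or more per week", and exclusion criterion 13 in Protocol 7.2 reads "Subject whose SBM frequency is 3 or more per week".

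**Rescue in Week 1.** SAP 7.8.1 states: "Since rescue medication use will be disallowed during Week 1, the SBM frequency should equal the BM frequency". Its next sentence gives SBMs as the basis of analysis for protocol violators. Protocol 6.1, 7.3.2.1, 8.1.1.2 and 9.3.2, and the SAP's own section 4.2, bar rescue only from 24 hours before to 48 hours after the first dose.

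**Excluded medications.** SAP 7.2 also removes subjects for "Use of any excluded medications, procedures or treatments prior to the assessment of the primary endpoint". Protocol 13.1.1 carries the same bullet word for word. On later-line rescue, Protocol 6.1 says "The recommendation may include a medication from the excluded medication list", apart from four named agents or classes. Protocol 7.3.2.1 describes bisacodyl and glycerin rescue under the heading "Exceptions to Excluded Medications".

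**The concern.** The PPS repeat of the van Elteren test is a planned sensitivity analysis of the primary endpoint (SAP 7.8.1), so its membership rules should match the protocol. An SBM excludes any movement within 24 hours after rescue; a BM does not. If the PPS is programmed from the SAP bullet as printed, rescue-induced movements in screening count toward a limit that the protocol sets on spontaneous ones. Subjects who met every entry criterion and used rescue as allowed could then be left out.

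The Week 1 sentence is a different kind of error. It describes a trial in which no compliant subject uses rescue before Day 8, and it suggests that anyone who does is a violator. That is not the protocol's rule, and it could mislead whoever classifies deviations or checks the endpoint derivation.

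**Working it through.** **1. The plan's own sample size.** Inputs from SAP 6.0: means 4 and 5.9, SD 4, two-sided alpha 0.05, power 90%, Wilcoxon-Mann-Whitney test. With n per arm, take the effective size m = n × 3/π (the test's asymptotic relative efficiency under normality), and use two-sample noncentral-t power with noncentrality (1.9/4) × √(m/2) and 2m − 2 degrees of freedom. The smallest n with power of at least 0.90 is 99 per arm. The total is 198 at power 0.901, which matches the plan. It rests on SBM frequency and does not change.

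**2. How far a subject must be from the BM limit.** This assumes that the limit is averaged over the 14 screening days; the bullet gives no window. Three per week is 3 × 2 = 6 movements in 14 days. Baseline means in Protocol Table 4.a run from 1.28 to 1.68 SBMs per week.

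| SBMs per week | SBMs in 14 days | Rescue BMs needed to reach 6 |
|---|---|---|
| 1.28 | 2.56 | 3.44 |
| 1.68 | 3.36 | 2.64 |
| 2.5 (eligible, near the limit) | 5 | 1 |

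A typical subject needs about 3 or 4 rescue movements to be dropped. A subject at 2.5 needs one.

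**3. Share of Week 1 open to rescue.** Week 1 is 168 hours from the first dose. After the 48-hour ban, 168 − 48 = 120 hours remain (120/168 = 71%). If the three days without an adequate movement are counted from the first dose, 168 − 72 = 96 hours remain (57%).

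**4. Is rescue really available in the treatment period?** Protocol 6.1 and SAP 4.2 tie the three-day bisacodyl rule to the Screening Period. Protocol 2.0, 7.3.2.1 and 8.1.1.2 and SAP 7.6 apply it to the whole study. Prescriptions can be given on Days -1, 8 and 15 (Protocol 9.3.2, 9.3.3, Appendix A), rescue use is checked by diary at Day 8, and the double-blind diary asks about rescue every day (SAP 7.7). A ban that ends at 48 hours also implies that use is allowed afterwards.

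**5. Does any of this reach the primary result?** The formula in SAP 7.8.1 is 7 × SBMs/days, and SAP 7.8 defines the blackout after rescue (24 hours, or 48 hours from midnight if the hour is missing). Neither depends on whether the user is a violator. The analysis is on the FAS, which is all randomized subjects. The answer is no.

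**6. Illustration for the PPS.** The documents give no rescue or exclusion rates. With the formula in step 1, equal loss in both arms and the planned effect, dropping 5% (94.05 per arm) gives power 0.886, and dropping 10% (89.1 per arm) gives 0.869, against 0.901 with none dropped. The percentages are assumptions.

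**The case against.** The best defense is that the BM bullet has simply lost a letter. It stands under a stem about violated exclusion criteria, and a subject with fewer than three SBMs has violated none. The neighboring SAP bullet and the inclusion bullet both say SBM, and SAP 7.13 announces no such change. That is very likely what the authors meant. It does not make the text right: another bullet in this list, on dose adjustment, also differs from the protocol, and there the SAP version is the sensible one. A programmer therefore cannot assume that the protocol wording prevails wherever the two differ.

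There are also safeguards: a blinded data review, documented and signed reasons for exclusion, tabulated reasons, and definitions of major deviations promised before unblinding (Protocol 13.1, 13.1.1; SAP 7.2, 7.3). These would expose a wrong exclusion and could correct it, so they limit the risk. The data review meeting clause itself covers other events, not listed bullets.

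Finally, the Week 1 sentence changes no result: SAP 4.2 gives the correct window and no SAP sentence links the misstatement to PPS membership. That is accepted, and it is why this part is a correction of fact and not a threat to the analysis.

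**Conclusion.** Two SAP statements are wrong as written: the BM limit in the PPS list, and the claim that rescue is barred throughout Week 1. Only the first can change an analysis, and only the supportive one. Its size is unknown without rescue rates. Step 2 suggests that it would mainly touch subjects close to three SBMs per week or with repeated screening rescue. This is a low-priority correction, worth making because it is so cheap.

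A reader might infer three stronger points that the documents do not support:

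- **That the excluded-medication bullet contradicts the protocol's PP definition.** It is the same in Protocol 13.1.1, so it is an ambiguity that both documents share. Bisacodyl and glycerin are best read as exempt, given the heading in Protocol 7.3.2.1 and the separate bullet "Received treatment with a rescue medication within 24 hours prior to the first dose on the morning of Day 1", which would otherwise be redundant. Later-line rescue from the excluded list is the unclear part; since bisacodyl and glycerin must fail first, few subjects are likely.
- **That the primary analysis would count BMs for compliant rescue users,** because SAP 7.8.1 names SBMs only for violators. The endpoint definition, formula and blackout rules apply to everyone.
- **That the PPS estimate would be biased in a known direction or by a known amount.** Nothing in the documents allows either to be stated.

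**What to change.** Before unblinding:

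1. **SAP 7.2:** in the frequency bullet, change BM to SBM.
2. **SAP 7.8.1:** replace the Week 1 sentence with a statement that rescue is not permitted from 24 hours before to 48 hours after the first dose, and replace the sentence on protocol violators with one saying that the analysis is based on SBMs for all subjects.
3. **Deviation definitions promised in SAP 7.2 and Protocol 13.1.1:** state whether rescue permitted by Protocol 6.1 and 7.3.2.1 counts as an excluded medication for the PPS. Settling it there avoids making the SAP bullet differ from its twin in the protocol. Do not add an exclusion for rescue up to 48 hours after first dose under this heading; no listed bullet names it, so it would be a new PPS rule.

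The cost is a few words in two SAP sections and one line in a document already planned. No protocol amendment, extra table, subject or procedure is needed.

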7.3 DISPOSITION OF SUBJECTS

A summary of screened subjects will display the number of subjects screened and the number of subjects in the Total Set, FAS, SAF and PPS; overall and at each center. Reason for exclusion from each analysis population will also be presented.

Subject disposition will be summarized for the Total Set and will include the frequency and percentage of subjects who completed each visit, the frequency and percentage of subjects who were screen failures, the frequency and percentage of subjects who discontinued prematurely from the study along with the frequency and percentage of subjects for each reason for screen failure/discontinuation. This information will be displayed by treatment.

The primary reason for screen failure should be recorded using the following categories:

1. Pretreatment event (PTE) or adverse event (AE),
2. Did not meet inclusion criteria or did meet exclusion criteria.
3. Significant protocol deviation.
4. Lost to follow-up.
5. Voluntary withdrawal (specify reason).
6. Study termination.
7. Other (specify reason).

The primary reason for discontinuation should be recorded using the following categories:

1. PTE or AE, including liver function test (LFT) abnormalities.
2. Significant protocol deviation.
3. Lost to follow-up.
4. Voluntary withdrawal.
5. Study termination.
6. Pregnancy.
7. Lack of efficacy.
8. Unblinding of subject treatment.
9. Other.

CROSS-REGIONAL TEMPLATE

Template Number:	C-TMPL-DO-801	Page:	13 of 28
Version Number:	1.2	Effective Date:	14 Sep 2015
This version replaces:	1.1		
Parent Document:	C-SOP-DO-800		
Template Title:	Statistical Analysis Plan (Legacy Takeda)		

Significant protocol deviations for the FAS will be summarized according to the category of deviation, by site and treatment group.

